4.7. Conduct of Analyses

No analysis requiring statistical adjustment will be performed.

4.7.1. Sequence of analyses

The **final** analysis will be performed when all data up to study end are available. A CSR including all available data will be written and made available to the investigators at that time.

If the data for tertiary endpoints become available at a later stage, (an) additional analysis/ analyses may be performed. These data will be documented in annex(es) to the study report and will be made available to the investigators at that time.

4.8. Changes to Protocol Defined Analyses

The distribution analysis for antibody titers/concentration and scatter plots for individual immunogenicity data, which were originally planned statistical analysis specified in the protocol Amendment 1 (Dated: 15-MARCH-2022), are removed from this SAP as the sufficient relevant information has been obtained from other RSV MAT Phase I/II studies.

5. SAMPLE SIZE DETERMINATION

Approximately 378 maternal participants* will be randomized in a 2:1 ratio to achieve at least 340 evaluable maternal participants (including at least 16 evaluable adolescents from 15 to less than 18 YOA).

Participants who withdraw from the study will not be replaced.

**** Due to the recent safety signal in RSV-MAT-009, there will be no further enrollment and vaccination of maternal participants.***

5.1. Safety

A sample size of 252 participants in RSV-MAT vaccine group will provide a probability of 72%, 92% or 98% to observe at least one participant with AE, if the true AE rate is 0.5%, 1% or 1.5%, respectively.

Table 13 presents the precision one can get on the percentage of participants with AEs following dosing in study vaccine group.

If no AE was observed in RSV-MAT vaccine group, the exact, two-sided 95% confidence interval (CI) would rule out an AE rate of 1.5% or more. The current sample size also provides the precision on estimating the probability of observing AEs following dosing in RSV-MAT vaccine group. If 5% of the participants experienced an AE among 252 participants following vaccination with the RSV-MAT vaccine, an exact 95% CI would be (2.7%, 8.5%).

Table 13 Exact 95% confidence interval (CI) on the percentage of participants with adverse events (AEs) following dosing in RSV-MAT vaccine group

252 participants in RSV-MAT vaccine group		
Number (%) of participants with an AE	Exact 95% CI	
	Lower Limit	Upper Limit
0 (0)	0.0	1.5
3 (1)	0.2	3.2
5 (2)	0.7	4.6
8 (3)	1.3	5.9
10 (4)	1.9	7.2
13 (5)	2.7	8.5
15 (6)	3.4	9.7
18 (7)	4.2	10.9
20 (8)	5	12.1
23 (9)	5.8	13.2
25 (10)	6.6	14.4
38 (15)	10.8	20.0
50 (20)	15.2	25.5
63 (25)	19.8	30.8
75 (30)	24.4	36.1

Note: Precision estimation using PASS2019 19.0.1 (Confidence Interval [CI] for one proportion) [Hahn, 1991]
Exact 95% CI computed based on Clopper/ Pearson formula [Newcombe, 1998]

5.2. Immunogenicity

With at least 226 evaluable maternal participants for immunogenicity in the RSV-MAT vaccine group (assuming a 10% non-evaluable rate), the current sample size can provide an adequate precision for estimating the fold increase.

Table 14 presents the precision estimation of the fold increase from Day 1 to delivery based on standard deviation (SD) of log₁₀ transformed titer for neutralizing antibody RSV-A and half width of the fold increase.

If at least a 9-12 fold increase from Day 1 to delivery in terms of RSV-A neutralizing antibody is anticipated, then assuming a log₁₀ SD of 0.4, a 95% CI for a 9-fold increase would be (7.6, 10.7), and a 95% CI for a 12-fold increase would be (10.1, 14.2).

Table 14 Precision estimation on fold increase and its 95% CI with 226 participants in RSV-MAT vaccine group

Standard Deviation ¹	Fold Increase from Day 1 to delivery	No. of participants in RSV-MAT vaccine group	Half Width h ²	95% LL	95% UL	Log ₁₀ Fold
0.3	5	226	0.056	4.4	5.7	0.699
0.3	6	226	0.056	5.3	6.8	0.778
0.3	7	226	0.056	6.2	8.0	0.845
0.3	8	226	0.056	7.0	9.1	0.903
0.3	9	226	0.056	7.9	10.2	0.954
0.3	10	226	0.056	8.8	11.4	1
0.3	11	226	0.056	9.7	12.5	1.041
0.3	12	226	0.056	10.5	13.7	1.079
0.4	5	226	0.074	4.2	5.9	0.699
0.4	6	226	0.074	5.1	7.1	0.778
0.4	7	226	0.074	5.9	8.3	0.845
0.4	8	226	0.074	6.7	9.5	0.903
0.4	9	226	0.074	7.6	10.7	0.954
0.4	10	226	0.074	8.4	11.9	1
0.4	11	226	0.074	9.3	13.0	1.041
0.4	12	226	0.074	10.1	14.2	1.079

¹ Standard deviation on log₁₀ transformed RSV-A neutralizing antibody titer based on previous studies on PreF2 vaccine.

CONFIDENTIAL

²Precision estimation using PASS2019 19.0.1 (Confidence Interval [CI] for one mean) [[Hahn, 1991](#)]
 $LL=10^{(\log_{10}(\text{fold increase})-\text{half width})}$; $UL=10^{(\log_{10}(\text{fold increase})+\text{half width})}$

6. SUPPORTING DOCUMENTATION

6.1. Appendix 1 Study Population Analyses

6.1.1. Participant Disposition

Participant disposition will be summarized by group using descriptive statistics:

- Number of maternal participants screened, randomised, exposed and withdrawn including withdrawal reasons in each group and overall will be tabulated.
- Number of infant participants enrolled and withdrawn including withdrawal reasons will be tabulated by group, by sub-cohort within each group and overall.

6.1.2. Demographic and Baseline Characteristics

6.1.2.1. Analysis of demographics/baseline characteristics planned in the protocol

These analyses will be performed on the Exposed set and on the Per protocol for immunogenicity.

For all maternal participants, demographic characteristics (e.g., age at study intervention administration (<18 years; \geq 18 years; overall), gestational age at study intervention administration (<28^{0/7}; \geq 28^{0/7} weeks), geographic ancestry) will be summarized by group using descriptive statistics. The interval in days between maternal study intervention and delivery will be calculated and summarized by group using descriptive statistics.

For their infants, demographic characteristics (e.g., gestational age at time of delivery (\geq 37 weeks; <37 weeks), sex, weight, length, head circumference, geographic ancestry, APGAR score), and lifestyle characteristics (e.g., living environment, household composition, breastfeeding, passive smoking and extent of contact with children less than 6 YOA) will be summarized by group, and for each immunogenicity sub-cohort within each group, using descriptive statistics.

- Frequency tables will be generated for categorical variable such as geographic ancestry.
- Mean, median, SD and range will be provided for continuous data such as age.

6.1.2.2. Additional considerations

Demographic characteristics for maternal and infant participants will also be summarized on Enrolled Set for web public disclosure.

Subgroup analysis for demographic characteristics by age category at study intervention administration (<18 years; \geq 18 years; overall) for maternal participants and by

gestational age at birth (≥ 37 weeks; < 37 weeks) for infant participants will also be performed on Exposed Set and PPS.

Subject disposition will be summarized by group using descriptive statistics:

- Number of maternal participants screened, randomised, exposed and withdrawn including withdrawal reasons in each group and overall will be tabulated.
- Number of infant participants enrolled and withdrawn including withdrawal reasons will be tabulated by group, by sub-cohort within each group and overall.

Summary of past medical history and current medical conditions will be performed on Exposed Set by Medical Dictionary for Regulatory Activities (MedDRA) term. Un-coded medical conditions or medical history will be summarized under 'Other' category.

Vaccination history will be coded using GSK Drug dictionaries. Summary of vaccination history will be performed on Exposed Set by group.

6.1.3. Protocol Deviations

Important protocol deviations will be summarized based on Exposed Set by group.

Protocol deviations will be tracked by the study team throughout the conduct of the study. These protocol deviations will be reviewed to identify those considered as important as follows:

- Data will be reviewed prior to unblinding and freezing the database to ensure all important deviations (where possible without knowing the study intervention details) are captured and categorised in the protocol deviations dataset.
- This dataset will be the basis for the summaries of important protocol deviations.
- The summary will include number and percentage of participants with important protocol deviations by deviation category for each study group.
- An individual listing of protocol deviation will also be provided.

Protocol deviations which result in exclusion from the analysis set will also be summarized based on Exposed Set by group.

- Data will be reviewed prior to unblinding and freezing the database to ensure all deviations leading to analysis population exclusions are captured and categorised in the protocol deviations ADaM dataset (note these exclusions are not captured in the SDTM dataset).

In addition to the overall summary of important protocol deviations, separate summaries may be produced for important protocol deviations related to COVID-19, and important protocol deviations not related to COVID-19 respectively if deemed necessary.

Summary of important protocol deviations leading to elimination will be tabulated by group. An individual listing will also be provided.

6.1.4. Concomitant Medications and Vaccinations

Concomitant medications and vaccinations will be coded using the GSK Drug dictionary.

- The number and percentage of maternal participants taking concomitant medications /vaccinations within 7 days following vaccination, 30 days following study intervention administration, up to 42 days post-delivery and up to 180 days post-delivery will be summarized by group. A listing will also be provided.
- The number and percentage of infants taking concomitant medications from birth up to 42 days after birth, 180 days after birth and 365 days after birth will be summarized by group. A listing will also be provided.
- The number and percentage of infants taking concomitant vaccinations from birth up to 42 days after birth and 180 days after birth will be summarized by group. A listing will also be provided.

6.1.5. Additional Analyses Due to the COVID-19 Pandemic

Depending on how the Covid-19 situation evolves, the SAP might be amended to reflect the analysis corresponding to Covid-19.

6.2. Appendix 2 Data Derivations Rule

6.2.1. Study Day and Reference Dates

The safety reference date is the study intervention start date and will be used to calculate study day for safety measures.

The study day is calculated as below:

- Assessment Date = Missing → Study Day = Missing
- Assessment Date < Reference Date → Study Day = Assessment Date – Ref Date
- Assessment Date ≥ Reference Date → Study Day = Assessment Date – Ref Date + 1

6.2.2. Attributing events to vaccine doses

The dose relative to an event is the most recent study dose given to a participant prior to the start of a given event.

If an event starts on the same day as a study dose, the relative dose will be derived from the additional information provided in the case report form (CRF) using the contents of the flag indicating if the event occurred before or after study dose. If ‘after study dose’ is selected, the relative dose for the event will be the one administered on the start day of the event. If ‘before study dose’ is selected, the relative dose for the event will be the dose prior to this one.

6.2.3. Handling of missing data

6.2.3.1. Dates

When partially completed dates (i.e. dates missing a day and/or month) are used in calculations, the following standard rules will be applied:

- A missing day will be replaced by 15
- A missing day and month will be replaced by June 30th.

The following exceptions apply:

- Adverse event start dates with missing day:
 - If the event starts in the same month as at least one of the study doses, the contents of AE.AESTRTPT (the flag indicating if the event occurred before or after study dose) will be used to complete the date. If ‘after study dose’ is selected, the imputed start date will match the first (or only) study dose given during that month. If ‘before study dose’ is selected, the imputed date will be one day before the first (or only) study dose given during that month.
- Adverse event start dates with missing day and month:
 - If the event starts in the same year as at least one of the study doses, the contents of AE.AESTRTPT (the flag indicating if the event occurred before or after study dose) will be used to complete the date. If ‘after study dose’ is selected, the imputed start date will match the first (or only) study dose given during that year. If ‘before study dose’ is selected, the imputed date will be one day before the first (or only) study dose given during that year.

All other cases of incomplete AE or concomitant medication/vaccination start date will follow the standard rules above.

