Study intervention Assignment	
Study intervention schedule*: 1 single dose administered IM between 24 and 36 weeks of gestation (at Visit 1, Day 1) to maternal participants.
 
* Due to the recent safety signal, there will be no further enrollment and vaccination of maternal participants.
 
Randomized study intervention allocation* is 2:1 (investigational vaccine: placebo), as described in Table 2.
 
* Due to the recent safety signal, there will be no further enrollment and vaccination of maternal participants.

Conduct of Analyses	
No analysis requiring statistical adjustment will be performed. However, analyses to evaluate objectives and endpoints will be performed in steps. Refer to Section 4.7 for details.

CONFIDENTIAL

Table 2 Study groups, intervention and blinding

Study groups	Maternal participants				Infant participants		Sub-cohorts for randomization (Allocation 1:1:1)	Blinding		
	~Number	Age in years (Min-Max)	Intervention name	Study groups for randomization (Allocation 2:1)	Infant Blood Sampling sub-cohorts			M + I Up to Day 43 post-delivery/birth	M + I Up to Day 181 post-delivery/birth	I only From Day 182 to Day 366 post-delivery/birth
					Name	~Number		Double-blind**	Single-blind**	Single-blind**
RSV_MAT	~252 *	15 – 49	RSV MAT	RSV_MAT	RSV_MAT_BS1	~84	RSV_MAT_BS1	•	•	•
					RSV_MAT_BS2	~84	RSV_MAT_BS2			
					RSV_MAT_BS3	~84	RSV_MAT_BS3			
Control	~126 *	15 – 49	Control	Control	Control_BS1	~42	Control_BS1	•	•	•
					Control_BS2	~42	Control_BS2			
					Control_BS3	~42	Control_BS3			

Control = Placebo; **M** = maternal participants; **I** = infant participants

Infant sub-cohorts are abbreviated “BS1”, “BS2” and “BS3” correspond to Visit 2-NB (Day 43 post-birth), Visit 3-NB (Day 121 post-birth) and Visit 4-NB (Day 181 post-birth), respectively.

RSV_MAT_BS1, _BS2, _BS3 = infants born to women in the RSV_MAT group and evaluated for immunogenicity at the designated timepoint (Day 43, Day 121 or Day 181 post-birth).

Control_BS1, _BS2, _BS3 = infants born to women in the Control group evaluated for immunogenicity at the designated timepoint (Day 43, Day 121 or Day 181 post-birth)

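### Partial start dates for infant adverse events can be imputed to before birth, because the SAP's date rules have no floor at the date of birth

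*SAP*

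**What the plan says.** SAP 6.2.3.1 sets two standard rules for incomplete dates used in calculations: "A missing day will be replaced by 15" and "A missing day and month will be replaced by June 30th". It then gives two exceptions for adverse event start dates. If the event falls in the same month as a study dose and is flagged as occurring after it, "the imputed start date will match the first (or only) study dose given during that month"; the year-only exception works the same way by calendar year. Everything else goes back to the calendar rules: "All other cases of incomplete AE or concomitant medication/vaccination start date will follow the standard rules above".

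The neighbouring sections use the same anchor. SAP 6.2.1 reads "The safety reference date is the study intervention start date and will be used to calculate study day for safety measures". SAP 6.2.2 reads "The dose relative to an event is the most recent study dose given to a participant prior to the start of a given event". Only mothers are dosed, once and before delivery (SAP 1.2: "1 single dose administered IM between 24 and 36 weeks of gestation (at Visit 1, Day 1) to maternal participants").

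The infant primary safety endpoints in SAP 4.2.1.1 are counted from birth, to day 42 for AESIs and to days 42, 180 and 365 for SAEs, withdrawals due to events, and MAEs. The method cell for the 42-day SAE/withdrawal/MAE endpoint starts the count at Day 1 instead. Protocol 9.4.3.1 has the same mismatch.

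**The concern.** The dose exceptions exist because a mid-month or mid-year date can land on the wrong side of a date that matters. For infants that date is birth, and the same protection was not extended to it. Applied as written, the rules can give an infant an onset before the infant was born.

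Infant safety to one year was made a primary objective in Protocol Amendment 1, and the windows start at birth. A programmer who applies the window literally would leave a pre-birth onset out; another might keep it. The study is fully unblinded, so a decision taken case by case would be made with allocation known. The infant concomitant medication and vaccination summaries in SAP 6.1.4 also run from birth and use the same start-date rule.

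**Working it through.** The documents state no figure on date imputation and no rate of partial dates, so there is nothing of theirs to reproduce. The check applies the rules to one case and then counts.

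**Inputs.** The two calendar rules and the dose exceptions (SAP 6.2.3.1); one maternal dose before delivery (SAP 1.2); windows from birth (SAP 4.2.1.1). Assumptions not in the documents: births evenly spread over 365 days; onset evenly spread over the stated days after birth. The main count treats infants as having no study dose, as SAP 6.2.2 suggests.

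**One case.** Mother dosed 10 October 2021, infant born 20 January 2022, event recorded as January 2022. No dose falls in that month, so the exception cannot apply on any reading. Imputed onset is 15 January: 15 − 20 = −5 days relative to birth.

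**Missing day.** An event with onset *o* days after birth is dated before birth when the birth falls after the 15th and the onset is still in the birth month. A month of *L* days has *L* − 15 − *o* such birth dates (zero if negative).

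- Onset on the day of birth: 365 − 12 × 15 = 185; 185/365 = 50.7%.
- Onset days 0-6: 7 × 185 − 12 × (0+1+…+6) = 1,295 − 252 = 1,043; out of 7 × 365 = 2,555 this is 40.8%.
- Longer spans: each 31-day month contributes 16+15+…+1 = 136, each 30-day month 120, February 91. The total is 7 × 136 + 4 × 120 + 91 = 1,523. For days 0-27, 1,523/10,220 = 14.9%; for days 0-42, 1,523/15,695 = 9.7%.

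The calendar month of birth matters little here: for onset on the day of birth the share runs from 13/28 = 46.4% (February) to 16/31 = 51.6%.

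**If the mother's dose were taken as the infant's study dose.** Enumerating dose-to-birth gaps of 8 to 112 days (planned delivery within 7 days is excluded by Protocol 5.2.1.1; 24 to 40 weeks is 112 days) gives 51.6%, 41.7% and 10.1% for day 0, days 0-6 and days 0-42. The dose exception adds under 1 percentage point overall, nothing for gaps of 28 days or more, and 2.0 to 4.6 points for gaps of 8-27 days.

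**Missing day and month.** Onset is dated before birth when birth is after 30 June and onset is in the same year: 184 − *o* birth dates. Over days 0-42 this is 43 × 184 − 903 = 7,009; 7,009/15,695 = 44.7%, or 77.8% by enumeration if the mother's dose counts. These two figures are illustrative only. Vaccination stopped on 25 February 2022 (Protocol 2.3). A dose at 24 weeks on that day reaches 40 weeks 112 days later, on 17 June 2022, so nearly all 2022 births should precede 30 June. The affected births are those in the second half of 2021, and the documents do not give their share.

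**The case against.** The strongest reply is that the practical effect is close to nil. SAEs and AESIs must be reported within 24 hours (Protocol 8.3.1 and Table 18), infants are followed by frequent active contacts and scheduled visits, and source data are verified. Year-only onsets in such infants should be rare. The rules are the same in both groups and every analysis is descriptive, so no bias between groups has been shown. All of that stands and limits the size of the point. It does not make the imputed date valid.

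Four stronger readings are tempting, and the documents do not support them:

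- *The maternal dose causes the error.* For missing-day dates the fixed 15th does nearly all of it. The exception reaches infants only if the mother's dose is treated as theirs, which the SAP does not say and SAP 6.2.2 speaks against.
- *Events are dropped.* The SAP has no rule excluding an infant event with an imputed pre-birth onset. Infant events are collected only from birth, by-participant listings are planned, and the Day 1 wording could keep such events in the 42-day SAE/MAE table. Loss is what a literal window would produce, not a stated step.
- *Infant windows have no birth anchor.* The endpoint text does anchor them at birth. What is missing is a birth reference in the study-day and imputation rules.
- *It hits the safety signal.* The RSV MAT-009 signals were preterm birth and neonatal death (Protocol 2.3). The first is fixed by the birth itself and the second is reported urgently; both are among the events least likely to have partial dates.

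**Conclusion.** The gap is real but minor. Followed as written, the rules can give an infant event an impossible onset date, and the SAP does not say what happens to it. For missing-day events the share dated before birth is about 51% with onset on the day of birth, about 41% for days 0-6 and about 10% over days 0-42. These are shares of partial-date events, not of all events, and they assume births and onsets evenly spread. The number of partial dates is unknown. That it will be small, and mostly non-serious MAEs, is a judgement based on the reporting rules. No change to a conclusion of the trial is shown.

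**What to change.** In SAP 6.2.1, state that for infant records the reference date is the date of birth, and name the variable that holds it. Protocol 5.3.1 collects only month (where allowed) and year of birth as demographic data, so the recorded delivery date may have to serve. In SAP 6.2.3.1, set any imputed infant onset earlier than birth to the date of birth, and say that the dose-based exceptions apply to maternal records only. In the infant 42-day SAE/withdrawal/MAE method cell of SAP 4.2.1.1, start the count at birth instead of Day 1.

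The cost is a few sentences and one derivation line, with no new data. The share imputed before birth then becomes zero by construction. The floor does not affect events pushed the other way: under the same assumptions, 12 × (1+2+…+14) = 1,260 of 15,695, or 8.0%, of missing-day events with true onset on days 0-42 would be dated after day 42.

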6.2.3.2. Laboratory data

Missing laboratory results (including immunological data) will not be replaced.

6.2.3.3. Daily recording of solicited events

6.2.3.3.1. Studies with electronic diaries

For studies using electronic diaries for the collection of solicited events, a solicited event will be considered present only when a daily recording of grade 1 or more is present.

6.2.3.4. Unsolicited adverse events

Unsolicited AE summaries are including SAEs unless specified otherwise.

Missing severity, relationship with study intervention, and outcome of unsolicited AEs will not be replaced and will appear as 'UNKNOWN' when displayed in a statistical output.

6.2.4. Data derivation

6.2.4.1. Age at first dose in years

When age at first dose is to be displayed in years, it will be calculated as the number of complete calendar years between the date of birth and the date of first dose. For example:

DOB = 10SEP1983, Date of first dose = 09SEP2018 -> Age = 34 years

DOB = 10SEP1983, Date of first dose = 10SEP2018 -> Age = 35 years

